2. INTRODUCTION

This intervention-specific appendix (ISA) describes a Phase 2 study of JNJ-73763989 (JNJ-3989) in combination with a nucleos(t)ide analog (NA) and pegylated interferon alpha-2a (PegIFN- α 2a). It is a companion document to the Master Protocol PLATFORMPAHPB2001, which describes the Sponsor's Platform study in participants with chronic HBV infection. This ISA describes specific and/or additional protocol elements applicable to this intervention cohort.

JNJ-3989 is a liver-targeted antiviral therapeutic for subcutaneous injection designed to treat chronic hepatitis B virus (HBV) infection via a ribonucleic acid interference (RNAi) mechanism. Engagement of the cellular RNAi machinery by JNJ-3989 results in specific cleavage of HBV RNA transcripts, thereby reducing the levels of HBV proteins and the pre-genomic ribonucleic acid (pgRNA), the precursor of viral relaxed circular deoxyribonucleic acid (rcDNA). The small interfering RNA (siRNA) triggers in JNJ-3989, JNJ-73763976 (JNJ-3976) and JNJ-73763924 (JNJ-3924), are designed to target all HBV ribonucleic acid (RNA) transcripts derived from covalently closed circular deoxyribonucleic acid (cccDNA), as well as transcripts derived from integrated HBV deoxyribonucleic acid (DNA). The latter has been suggested to be a significant source of hepatitis B surface antigen (HBsAg) in hepatitis B e antigen (HBeAg)-negative patients or patients on long-term (≥ 2 years) treatment with NAs, the current standard of care ([Wooddell 2017](#)).

Select NAs and PegIFN- α 2a are approved treatments of chronic HBV infection.

For the most comprehensive nonclinical and clinical information regarding JNJ-3989, refer to the latest version of the Investigator's Brochure (IB) for JNJ-3989 ([IB JNJ-3989](#)). For nonclinical and clinical information regarding NA and PegIFN- α 2a, refer to their respective prescribing information.

An introduction on HBV and the current treatment options is provided in Section 2 of the Master Protocol PLATFORMPAHPB2001.

The term "study intervention" throughout the protocol, refers to JNJ-3989, NA, and PegIFN- α 2a as defined in Section 6.1, Study Intervention(s) Administered.

The term "Sponsor" used throughout this document refers to the entities listed in the Contact Information page(s), which will be provided as a separate document.

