7.1. Discontinuation of Study Intervention

Treatment with JNJ-3989 (and PegIFN- α 2a if applicable) must be discontinued prematurely if any of the discontinuation criteria listed below are met. Criteria specific for this ISA are highlighted (colored fill). For the few criteria from the Master Protocol that are specified or more restricted in this ISA, the changes compared to the Master Protocol are also highlighted (colored fill). If JNJ-3989 is prematurely discontinued, PegIFN- α 2a (if applicable) should also be discontinued. If PegIFN- α 2a is prematurely discontinued (ie, before Week 23 [Arms 1 and 2] or before Week 11 [Arm 3]), treatment with JNJ-3989 and NA should be continued as planned. NA treatment may be continued or, in consultation with the Sponsor, discontinued based on investigator judgement.

The discontinuation criteria are:

- The participant withdraws consent to receive study intervention.
- The investigator believes that for safety or tolerability reasons (eg, AE) it is in the best interest of the participant to discontinue JNJ-3989 (and PegIFN- α 2a, if applicable).
- The participant becomes pregnant.
- The participant has a \geq Grade 3 rash (see Section 10.6, Appendix 6: Rash Management) or allergic reaction (see Section 8.3.7.3, Acute Systemic Allergic Reactions).
- The participant has signs of hepatic decompensation (ie, clinical evidence of ascites, bleeding varices, or hepatic encephalopathy) or an increase in direct bilirubin $>1.5\times$ ULN in combination with INR $\geq 1.5\times$ ULN or albumin <3.0 g/dL. Treatment with JNJ-3989 should be discontinued and alternative treatment options (outside the study) should be considered in discussion with the Sponsor.
- The participant has a confirmed \geq Grade 3 eGFR abnormality and a drop from baseline of >10 mL/min/ 1.73 m², considered at least possibly related to JNJ-3989 (or PegIFN- α 2a, if applicable) that persists despite changing tenofovir disoproxil to ETV or TAF (if the patient was receiving tenofovir disoproxil) (see Section 8.3.7.2, Renal Complications).
- The participant has a QTcF prolongation (defined as a QTcF value of >500 ms, or an increase from baseline of >60 ms) at any given time point.
- The participant requires ≥ 7 days of treatment with any of the disallowed medications listed in Section 6.8, Concomitant Therapy, and does not intend to discontinue treatment with the disallowed medication.

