8.3.6.2. Intervention-emergent ALT/AST Elevations

Elevated liver enzyme activity can be triggered by the underlying HBV disease as well as by the study intervention.

Management of intervention-emergent ALT/AST elevations is presented graphically in Section [10.7](#), Appendix 7: Intervention-emergent ALT/AST Elevations, and is described below.

Any intervention-emergent elevation of ALT and/or AST $\geq 3x$ ULN and $\geq 3x$ nadir (ie, lowest value during study participation) should trigger an assessment of confounding factors (alcohol intake, change in concomitant medication, and comorbidities) and should trigger a confirmatory study visit to repeat laboratory testing of AFP, ALT, AST, ALP, bilirubin (total and direct), INR, albumin, and HBV DNA. Additional tests should be considered based on clinical judgement (refer to Section [10.7](#), Appendix 7: Intervention-emergent ALT/AST Elevations). This confirmatory visit should be scheduled as soon as possible within 7 days of the receipt of the initial ALT/AST results. In case the repeat laboratory testing shows an isolated ALT/AST elevation (ie, with stable albumin, bilirubin [total and direct], and INR) the participant may continue study intervention. In case of confirmed ALT elevation $>1,000$ U/L and $\geq 3x$ the baseline value, JNJ-3989 (and PegIFN- $\alpha 2a$ if applicable) should be discontinued. In both cases, NA treatment should be continued. The participant will be monitored (laboratory testing of AFP, ALT, AST, ALP, bilirubin [total and direct], INR, albumin, and HBV DNA) on a weekly basis or more frequently until ALT and AST levels have returned to $<5x$ ULN and HBV DNA is $<20,000$ IU/mL. Additional PBMC and AFP samples may be taken in case of ALT flares, upon discussion with the Sponsor, which may require an unscheduled visit.

If the ALT and/or AST level is $\geq 3x$ ULN and $\geq 3x$ nadir and is associated with any of the following laboratory results or clinical symptoms:

- INR ≥ 1.5 , OR
- direct bilirubin $> 1.5x$ ULN, OR
- serum albumin < 3.0 g/dL, OR
- ascites, hepatic encephalopathy, or liver-related symptoms (eg, severe fatigue, nausea, vomiting, right upper quadrant pain in the absence of an alternative medical explanation), OR
- other indication of reduced liver function,

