8.3.6.3. Hematologic Abnormalities

In the Phase 1/2a AROHBV1001 study with JNJ-3989, mild (Grade 1) transient thrombocytopenia was observed in 6 out of 84 participants receiving 3 subcutaneous injections of JNJ-3989 alone over a period of up to 12 weeks with background of NAs. The transient thrombocytopenia was not considered clinically significant. No thrombocytopenia or pancytopenia was observed in 12 participants when JNJ-3989 was given in combination with JNJ-6379 over a 12-week period in the same study.

Based on the non-clinical findings, any relevant abnormalities in hematologic parameters will be carefully monitored as described below:

- Platelet counts: $< 100,000$ cells/mm³ (at least Grade 2 [DAIDS]) or < 100 GI/L or reduction from baseline by at least 50%.
- Hemoglobin: Decrease of at least 2 g/dL from baseline or at least Grade 2 (DAIDS).
- Neutrophil count: Treatment-emergent reduction to at least Grade 2 (DAIDS).

In case any of the above criteria are met, a confirmatory visit should be scheduled as soon as possible, preferably within 7 days of the receipt of the initial results. Confirmation of the results will trigger weekly or biweekly (every other week) unscheduled visits until improvement or

stabilization of the respective parameter(s). Stabilization is defined as no further significant reduction over two consecutive visits.

In case of confirmed Grade 3 or Grade 4 hematologic abnormalities, discontinuation of JNJ-3989 (and PegIFN- α 2a if applicable) should be considered. In case of discontinuation, NA treatment should be continued.

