8.3.7.1. Rash

Participants should be informed that they should contact their doctor immediately when they notice any generalized skin reaction. This skin reaction should be evaluated in the clinic the same day (if possible) or the next possible day.

All rash events should be captured in the AE section of the CRF. Separate Rash pages will be completed in case of a rash event.

Monitoring of the evolution of rash events will be performed as described in Table 4 in Section 10.6, Appendix 6: Rash Management.

When safety blood samples are drawn as per the rash management guidelines, these should be processed by the local laboratory. The following parameters will need to be tested: AST, ALT, sedimentation rate, complete blood cell count (including hemoglobin, hematocrit, RBC count, WBC count, differential count [neutrophils, lymphocytes, monocytes, eosinophils, and basophils], and platelet count), and creatinine. The values of the local laboratory assessments need to be transcribed in the CRF by the study site personnel.

The participant may be treated symptomatically until the rash resolves. Oral antihistamines (eg, cetirizine, levocetirizine) and/or topical corticosteroids may provide symptomatic relief but effectiveness of these measures has not been established. If systemic corticosteroids exceeding 5 mg of prednisolone equivalent/day are required for treatment of rash, JNJ-3989 (and PegIFN- α 2a if applicable) need to be permanently discontinued. NAs can be continued. If the rash is considered to be most likely due to concomitant illness or non-study interventions, standard management, including discontinuation of the likely causative agent, should be undertaken.

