8.3.7.2. Renal Complications

If renal complications develop, participants should be closely monitored for disturbances in creatinine clearance. Additional investigations can be performed at the investigator's discretion. Participants must be treated as clinically appropriate.

Participants who develop confirmed Grade 3 or 4 eGFR abnormalities with reduction from baseline by at least 10 mL/min/1.73 m² will change their NA from tenofovir disoproxil to ETV or TAF (if the patient was receiving tenofovir disoproxil), according to the prescribing information. If the abnormality persists despite change of NA or if the patient is not receiving tenofovir disoproxil, he or she will permanently discontinue the intake of JNJ-3989 (and PegIFN- α 2a if applicable) if considered at least possibly related to JNJ-3989 (or PegIFN- α 2a if applicable) and should be followed appropriately until resolution of the AE or toxicity. Rechallenge is not allowed.

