ISR	injection site reaction
KPD	kinetic pharmacodynamic model
LLN	lower limit of normal
LLOQ	lower limit of quantification
MDSC	myeloid-derived suppressor cell
MoA	mode of action
MRI	magnetic resonance imaging
MRU	medical resource utilization
NA	nucleos(t)ide analog
NIMP	non-investigational medicinal product
NK	natural killer
NOAEL	no observed adverse effect level
PBMC	peripheral blood mononuclear cell
PD	pharmacodynamic(s)
PegIFN- α 2a	pegylated interferon alpha-2a
pgRNA	pre-genomic ribonucleic acid
PK	pharmacokinetic(s)
PoC	proof of concept
Q4W	every 4 weeks
QW	weekly
QD	once daily
QTcF	QT interval corrected for heart rate according to Fridericia's formula
RBC	red blood cell
rcDNA	relaxed circular deoxyribonucleic acid
RNAi	ribonucleic acid interference
SAE	serious adverse event
SAP	Statistical Analysis Plan
SD	standard deviation
SDM	site-directed mutant
SE	standard error
siRNA	small interfering ribonucleic acid
$t_{1/2\text{term}}$	terminal half-life
T4	thyroxine
TAF	tenofovir alafenamide
TEAE	treatment-emergent adverse event
t_{max}	time to reach C_{max}
TND	target not detected
TNF	tumor necrosis factor
TSH	thyroid stimulating hormone
WBC	white blood cell

Definitions of Terms

ALT/AST nadir	Lowest ALT/AST value during study participation
End of study intervention (EOSI)	Time of the last administration of study intervention
Functional cure (FC)	HBsAg seroclearance at 24-weeks after EOSI
HBsAg or HBeAg seroclearance	HBsAg or HBeAg negativity, respectively, based on the assay used
HBsAg or HBeAg seroconversion	HBsAg or HBeAg negativity and anti-HBs or anti-HBe antibody positivity, respectively
IC ₅₀	half maximal inhibitory concentration
Study intervention	JNJ-73763989 (JNJ-3989), NA (either ETV, tenofovir disoproxil, or TAF), and PegIFN- α 2a
Virologic breakthrough	Confirmed on-treatment HBV DNA increase by $>1 \log_{10}$ IU/mL from nadir or confirmed on-treatment HBV DNA level >200 IU/mL in participants who had HBV DNA level $<$ LLOQ of the HBV DNA assay.

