- For participants unable to visit the study site, direct-to-patient (DTP) shipment or handover to a caregiver or delegate of oral study intervention, as well as PegIFN- α 2a, may be implemented, where allowed per local regulations^a and if requested by the treating study physician. Where DTP shipments or handover to delegates are deemed necessary, the process must be coordinated between the site and Sponsor staff following standard DTP procedures for arranging shipment and adhering to associated approvals and documentation requirements.
- JNJ-3989 should always be administered by a nurse at the study site or, if site visits are not possible, at the participant's home. Refer to Section 6.4, Study Intervention Compliance, in case a scheduled administration of study intervention (JNJ-3989, NA, or PegIFN- α 2a) is missed.

Continuation of Study Intervention:

- Any issue with continuation and/or provision of study intervention should be discussed with the Sponsor and should be well documented.
- Study intervention should be continued if, in the assessment of the investigator, it does not result in risk to the participant. If at any time the participant's safety is considered at risk due to study intervention, study intervention will be temporarily or permanently discontinued,

^a Delivering PegIFN- α 2a is not applicable for sites in countries that do not allow PegIFN- α 2a self-injection.

while every effort should be made to maintain follow-up on study. The benefit of continuing study intervention should be assessed by the investigator for each individual participant, considering the potential impact of reduced direct clinical supervision on participant safety.

- If a participant develops a SARS-CoV-2 infection, the investigator should contact the Sponsor to discuss plans for study intervention and follow-up. A decision to continue study intervention should be made by the investigator depending on symptoms and concomitant medication(s) used for the treatment of COVID-19. Study intervention must be discontinued if prohibited medication is used.
- When a participant, for whom study intervention has been interrupted, recovers from suspected or confirmed SARS-CoV-2 infection or related disease and all adverse events (AEs) related to SARS-CoV-2 infection improve to Grade ≤ 1 , the investigator should discuss with the Sponsor about resuming study intervention.

COVID-19 vaccination during the study:

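### Read with the protocol's own definition, Appendix 10's SARS-CoV-2 bullet orders NA to be stopped on any use of a prohibited drug, in conflict with Sections 7.1 and 8.3.7.1 (minor, safety wording)

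*Protocol*

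**What the plan says.** Appendix 10 of the protocol, in its part on continuing study intervention, has a bullet for a participant who develops SARS-CoV-2 infection. It asks the investigator to contact the Sponsor. It makes continuation the investigator's decision, depending on symptoms and the drugs given for COVID-19. It then closes with "Study intervention must be discontinued if prohibited medication is used". That sentence names no agent, sets no minimum duration and makes no exception for NA.

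Section 2 says that the term study intervention "throughout the protocol, refers to JNJ-3989, NA, and" PegIFN-α2a. The definitions in Appendix 1 list the same three components. Appendix 10 also uses the term this way: its bullet on missed doses spells study intervention out as all three agents.

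Section 7.1 has its own criterion for disallowed medication. It applies when at least 7 days of such treatment are needed and the participant does not intend to stop the drug. Its consequence is that JNJ-3989 (and PegIFN-α2a, if applicable) stops. For NA the section says "NA treatment may be continued or, in consultation with the Sponsor, discontinued based on investigator judgement".

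Section 8.3.7.1 deals with a drug that Table 3 itself disallows, systemic corticosteroids above 5 mg prednisolone equivalent per day, when needed for rash. JNJ-3989 and PegIFN-α2a "need to be permanently discontinued. NAs can be continued".

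**The concern.** A site that applies the defined term to the Appendix 10 sentence would stop NA in an infected participant who receives any Table 3 drug. Section 2.3.2.2 names NA discontinuation as carrying a risk of hepatitis B flare. The current amendment added NA completion criteria after a severe flare following NA discontinuation in the REEF-2 control arm. Section 4.2 gives their purpose: only participants with better prospects off treatment should stop everything.

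A stop under Appendix 10 would bypass those criteria, possibly while the participant is on an immune-interfering drug and while site supervision is reduced. The restart rules in Section 6.5.2 are written for participants who met the completion criteria, so they do not clearly cover this participant.

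**Working it through.** No sample size, power or alpha figure enters this point. The check compares texts.

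**Step 1. Apply the definition.** Substituting the Section 2 and Appendix 1 definition into the Appendix 10 sentence gives: JNJ-3989, NA and PegIFN-α2a must all stop if prohibited medication is used.

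**Step 2. Compare triggers.** As an illustration (the documents do not say which drugs would be given for COVID-19), take 5 days of systemic corticosteroid above 5 mg/day.
- Appendix 10: prohibited medication has been used, so all three agents stop.
- Section 7.1: 5 days is below 7 days, so the criterion is not met and nothing stops on this ground.

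With 10 days and a planned end date, Section 7.1 is still not met, because it also requires no intention to stop the drug. If it were met, NA would still be optional.

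**Step 3. See what every other section on stopping JNJ-3989 or PegIFN-α2a says about NA.**

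| Section | Situation | NA |
|---|---|---|
| 6.5.1 | JNJ-3989 stopped early | Optional, with the Sponsor, by the completion criteria |
| 7.1 | All listed criteria, including disallowed drugs | Optional, investigator with the Sponsor |
| 8.3.6.2 | ALT/AST elevation | "In both cases, NA treatment should be continued"; the same where liver function is reduced |
| 8.3.6.3 | Hematologic | "In case of discontinuation, NA treatment should be continued" |
| 8.3.7.1 | Rash needing systemic corticosteroids | Can continue |
| 8.3.7.2 | Renal, on tenofovir disoproxil | Switched: participants "will change their NA from tenofovir disoproxil to ETV or TAF" |
| 8.3.7.3 | Allergic reaction | Optional, investigator with the Sponsor |
| Appendix 6, Table 4 | Grade 3 or 4 rash | Optional, investigator with the Sponsor |

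Tally: 2 continue + 1 can continue + 1 switch + 4 optional = 8 sections; 0 of 8 mandate an NA stop. The entries overlap, since several are also Section 7.1 criteria, and Section 8.3.7.2 does not say what happens to NA once JNJ-3989 has stopped. Regrouping changes the 8 but not the 0.

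**Step 4. Follow-up, on the broad definition.** Footnote o of the Schedule of Activities rules out JNJ-3989 and PegIFN-α2a in follow-up. NA is given only to those who could not stop it or who met the re-treatment criteria. Table 3 bans immune-interfering drugs to the end of follow-up. Section 6.5.1 tells participants who miss the completion criteria to stay on NA for the 48 weeks. Read broadly, the Appendix 10 sentence contradicts that instruction for an infected participant still on NA.

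**The case against.** The strongest reply is that the sponsor almost certainly means JNJ-3989 and PegIFN-α2a. Section 7.1 is headed as discontinuation of study intervention, yet its mandatory stops concern those two agents. End of study intervention is fixed at Week 24 although NA may go on. Table 3 separates bans that end with study intervention from bans that run through follow-up, and Section 6.1 classes NA as background. Usage is mixed, however: Section 4.2 speaks of stopping all study intervention in a sense that includes NA, and Appendix 10 lists all three agents. Probable intent is a reason to state it, because the written definition points the other way.

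The second reply is that safeguards surround the sentence. Its bullet opens with Sponsor contact. Appendix 10 asks for a benefit-risk consultation with the Sponsor before emergency provisions are used and says that the guidance does not override clinical judgement. It refers to the protocol's discontinuation procedures, though only where participation must end. Participants not continuing NA in follow-up have mandatory 4-weekly visits. All this stands and lowers the chance of harm. None of it says that NA continues.

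Three stronger readings are not supported:
- **A general rule on prohibited medication.** The sentence closes a bullet on SARS-CoV-2 infection and should be read in that setting.
- **In follow-up the sentence can only act on NA.** That holds on the broad definition. On the narrow usage, study intervention has already ended and the sentence has nothing to act on.
- **The primary result is at risk.** The SAP (Section 5.3.2) counts treatment discontinuation before Week 24 as non-response, but the documents give no frequency for this situation, so no effect can be sized.

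**Conclusion.** The sentence is wrong as written, at minor severity, as safety wording. Taken with the protocol's definition, it mandates an NA stop that none of the other sections requires. It also uses an any-use trigger where Section 7.1 sets a threshold of at least 7 days with no intention to stop the drug. The conflict over the trigger is with Section 7.1; Section 8.3.7.1 also stops JNJ-3989 without a duration threshold, but for rash. The conflict over NA is with both sections.

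The conclusion rests on giving the defined term its defined meaning. It extends to follow-up only on that reading, and there only to participants still on NA or who have restarted it. The number affected is neither stated nor estimable.

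**What to change.** Replace the Appendix 10 sentence with: *If prohibited medication is used to treat COVID-19, JNJ-3989 (and PegIFN-α2a, if applicable) must be discontinued when the disallowed-medication criterion in Section 7.1 is met; NA treatment should be continued unless the investigator, in consultation with the Sponsor, decides otherwise.*

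This names the agents, restores the Section 7.1 threshold and makes continued NA the default. Merely inserting the agent names would leave the any-use trigger in conflict with Section 7.1. The cost is one sentence in an amendment or clarification letter, with no added procedures, visits or participants.
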